8. STATISTICAL CONSIDERATIONS

8.1. Analysis Objectives and Endpoints

8.1.1. Analysis Objectives

The primary objective of this study is:

 To evaluate the safety and tolerability of SOF/ FDC for 12-24 weeks in subjects with advanced heart failure or lung disease

The secondary objective of this study is:

 To determine the antiviral efficacy of SOF/LDV FDC for 12-24 weeks in subjects with chronic HCV and advanced heart failure or lung disease as measured by sustained virologic response 12 weeks after discontinuation of therapy (SVR12 defined as HCV RNA < lower limit of quantitation 12 weeks post-treatment).

8.1.2. Primary Endpoint

The primary safety endpoint is the proportion of subjects who complete a full course of therapy. The primary efficacy endpoint is SVR12 (HCV RNA < lower limit of Quantification [LLoQ] 12 weeks after last dose of study drug).

8.1.3. Secondary Endpoints

The main efficacy endpoint will be the measurement of SVR12, 12 weeks after discontinuation of therapy. Secondary efficacy endpoints include SVR4, 4 weeks after discontinuation of therapy.

8.1.4. Safety Endpoints

In addition to the primary endpoint of completion of full course of therapy, safety endpoints will include rates of discontinuation for adverse events and serious adverse events. Safety will also be assessed with adverse events and laboratory tests.

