3. SUBJECT POPULATION

3.1. Treatment plan and regimen

Approximately 25 subjects with chronic HCV and advanced heart failure; and 25 subjects with chronic HCV and advanced lung disease will be enrolled. Subjects must have genotype 1, 4, 5 or 6 HCV. All subjects will receive SOF/LDV FDC. The duration of treatment will be 12 weeks for treatment naïve subjects with or without cirrhosis. All subjects will receive 12 weeks of the SOF/LDV FDC except for treatment experienced genotype 1 subjects with cirrhosis, who will receive 24 weeks of treatment. All subjects will continue in the study follow-up period for 12 weeks after treatment has been completed.

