3.3. Number of subjects and subject selection

A total of approximately 50 subjects will be enrolled. Approximately 25 subjects with advanced heart failure and 25 subjects with advanced lung disease will be enrolled.

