3.4. Inclusion criteria

All subjects must meet all of the follow HCV criteria:

- Genotype 1, 4, 5, or 6
- HCV RNA > 10³ IU/mL at screening
- Age ≥ 18 years
- Diagnosis of chronic HCV infection, defined as positive HCV antibody or HCV RNA more than 6 months prior to screening OR an assessment of fibrosis F2 or greater prior to screening.

Subjects in the advanced heart failure cohort must meet **ALL** HCV criteria, and all of the following criteria:

- New York Heart Association (NYHA) Class III or IV functional classification
 - NYHA Class III: Subjects with cardiac disease resulting in marked limitation of physical activity. They are comfortable at rest. Less than ordinary physical activity causes fatigue, palpitation, dyspnea, or anginal pain.

- NYHA Class IV: Patient with cardiac disease resulting in inability to carry on any physical activity without discomfort. Symptoms of cardiac insufficiency or of the anginal syndrome may be present even at rest. If any physical activity is undertaken, discomfort is increased.
- ejection fraction ≤ 30%
- hospitalized for heart failure in last 12 months

Subjects in the advanced lung disease cohort must have been diagnosed with chronic obstructive pulmonary disease (COPD) or interstitial lung disease (ILD) must meet **ALL** HCV criteria, and meet the following criteria for COPD or ILD:

- ILD criteria: diagnosis of interstitial lung disease with chronic supplemental oxygen requirement at rest and/or with exertion.
- COPD criteria (one of the following):
 - Forced expiratory volume (FEV1)< 30% predicted
 - OR any FEV1 with chronic supplemental oxygen requirement at rest and/or with exertion
 - OR any FEV1 with chronic hypercapnea (baseline partial pressure of arterial carbon dioxide [PaCO2] > 45)

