7.3. Serious Adverse Events

A serious adverse event (SAE) is defined as follows:

Any adverse drug experience occurring at any dose that results in any of the following outcomes:

- Death
- Life-threatening situation (subject is at **immediate** risk of death)
- In-patient hospitalization or prolongation of existing hospitalization (excluding those for study therapy or placement of an indwelling catheter, unless associated with other SAEs)
- Persistent or significant disability/incapacity
- Congenital anomaly/birth defect in the offspring of a subject who received medicinal product
- Other: medically significant events that may not be immediately life-threatening or result in death or hospitalization, but based upon appropriate medical and scientific judgment, may jeopardize the subject or may require medical or surgical intervention to prevent one of the outcomes listed above

Examples of such events are as follows:

- Intensive treatment in an emergency room or at home for allergic bronchospasm
- Blood dyscrasias or convulsions that do not result in hospitalization
- Development of drug dependency or drug abuse

Clarification of Serious Adverse Events

- Death is an outcome of an AE, and not an adverse event in itself. In reports of death due to "Disease Progression," where no other information is provided, the death will be assumed to have resulted from progression of the disease being treated with the medicinal product(s).
- The subject may not have been on medicinal product at the occurrence of the event. Dosing
 may have been given as treatment cycles or interrupted temporarily before the onset of the
 SAE, but may have contributed to the event.
- "Life-threatening" means that the subject was at immediate risk of death from the event as it
 occurred. This does not include an event that might have led to death if it had occurred with
 greater severity.
- Complications that occur during hospitalizations are AEs. If a complication prolongs the hospitalization, it is a SAE.
- "In-patient hospitalization" means the subject has been formally admitted to a hospital for medical reasons, for any length of time. This may or may not be overnight. It does not include presentation and care within an emergency department.

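### All-cause death is not a named safety endpoint, and deaths from 30 days after last dose to post-treatment Week 12 have no planned safety summary

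*Combined protocol and SAP*

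**What the plan says.** **Endpoints.** Section 8.1.2 makes completion of the full course the primary safety endpoint. Section 8.1.4 adds that "safety endpoints will include rates of discontinuation for adverse events and serious adverse events", with AEs and laboratory tests as further assessments. The synopsis gives the same three main items. Death, survival and vital status are named in none of sections 8.1 to 8.6.

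**Status of death.** Death is the first outcome listed in the SAE definition in section 7.3, but the clarification there states: "Death is an outcome of an AE, and not an adverse event in itself".

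**What is recorded.** Section 7.1 limits AE database entry to events leading to drug discontinuation or withdrawal. Section 7.2 limits the AE form to events leading to discontinuation.

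**Time windows.** The synopsis ends SAE collection 4 weeks after last dose. Sections 8.6 and 8.6.1 end the safety summaries and the treatment-emergent period 30 days after last dose. Section 3.1 runs longer: "All subjects will continue in the study follow-up period for 12 weeks after treatment has been completed".

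**Design.** There is no control group: "All subjects will receive SOF/LDV FDC" (section 3.1). On size, section 3.3 says "Approximately 25 subjects with advanced heart failure and 25 subjects with advanced lung disease will be enrolled". The heart failure cohort requires "New York Heart Association (NYHA) Class III or IV functional classification", together with a low ejection fraction and a heart failure hospitalization in the past year (section 3.4).

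**The concern.** Subjects are selected for severe heart or lung disease, so some deaths during 24 to 36 weeks of observation are plausible whatever the drug does. With no control arm, a reader of the safety results will want to know first how many subjects died, and when. The plan produces no such figure.

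Take a subject who finishes treatment and dies on post-treatment day 40. The primary safety endpoint counts that subject as a success. The death falls after SAE collection has closed and outside the treatment-emergent table. Correct classification by the site does not change this, because it is the windows that exclude the death. A cohort could therefore report full completion while deaths among its completers go untabulated.

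**Working it through.** The plan states no mortality rate, and no power or precision basis for 50 subjects, so there is no figure to reproduce. The check has three steps.

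**1. Where a death would appear**

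| Time of death | Planned place in the results | Separate death count? |
|---|---|---|
| On treatment | Non-completion (8.1.2; the 8.2.2 set keeps the subject in the denominator); SAE or AE discontinuation if so reported | No |
| Last dose to 30 days after | SAE or AE reporting only (SAE collection stops at 4 weeks) | No |
| 30 days after last dose to post-treatment Week 12 | No planned safety summary | No |

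The recording rules add to the problem. Once dosing has ended, a fatal event cannot lead to drug discontinuation, so the section 7.2 form rule would not take it. Only the word withdrawal in section 7.1 might cover it.

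**2. Length of the gap**

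Post-treatment follow-up is 12 × 7 = 84 days, and the summaries stop at day 30 after last dose, so the gap is 84 − 30 = 54 days.

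- 12-week course: total 84 + 84 = 168 days; 54/168 = 32%.
- 24-week course: total 168 + 84 = 252 days; 54/252 = 21%.
- With the 4-week SAE collection limit the gap is 84 − 28 = 56 days: 33% and 22%.

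**3. How many deaths might fall there**

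Annual mortality m is an assumption, shown from 5% to 40%. With constant daily hazard h = −ln(1 − m)/365.25, the probability of dying in the gap on a 12-week course is exp(−114h) − exp(−168h), where 114 = 84 + 30.

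- m = 5%: h = 0.0001404; 0.9841 − 0.9767 = 0.0074; × 50 = 0.37.
- m = 40%: h = 0.0013986; 0.8526 − 0.7906 = 0.0620; × 50 = 3.10.

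Expected deaths for 50 subjects, all on 12 weeks:

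| Assumed m | Day 0–168 | On treatment | In the gap | P(at least one in the gap) |
|---|---|---|---|---|
| 5% | 1.17 | 0.59 | 0.37 | 31.1% |
| 10% | 2.37 | 1.20 | 0.75 | 52.9% |
| 20% | 4.88 | 2.50 | 1.51 | 78.5% |
| 30% | 7.57 | 3.94 | 2.30 | 90.5% |
| 40% | 10.47 | 5.54 | 3.10 | 95.9% |

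The last column is 1 − (1 − p)^50, with p the gap probability. If all 50 received 24 weeks, the gap figures would run from 0.37 to 2.76. In a cohort of 25, one death is 1/25 = 4 percentage points.

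**What the added endpoint would show.** Exact (Clopper-Pearson) 95% intervals: 0/25 gives 0 to 13.7%; 3/25 gives 2.5 to 31.2%; 0/50 gives 0 to 7.1%; 3/50 gives 1.3 to 16.5%.

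**The case against.** The strongest reply is that death is not left out. It heads the SAE outcomes, and SAEs are an endpoint. The AE definition in section 7.1 applies regardless of relatedness and includes worsening of a pre-existing condition, so a fatal decompensation qualifies without a causality judgement. The reason for withdrawal goes into the database (section 9.1.7), individual data are listed (section 8.1.5), and AEs are still assessed at post-treatment Week 12 (section 5.2.7).

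This stands in part. A reader might infer that a death reaches the results solely through the investigator's AE classification. The documents do not support that: an on-treatment death lowers the completion proportion however it is classified, and a withdrawal reason is a second route. But neither route gives a planned death count, and a listing shows only what was entered. An assessment at Week 12 also does not help if the form, the database and the summaries have no place for the event.

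A reader might also take the whole lung cohort to be oxygen-dependent. It need not be. A COPD subject may enter on "Forced expiratory volume (FEV1)< 30% predicted" alone, or under "OR any FEV1 with chronic hypercapnea".

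Three further objections are fair. The mortality range has no source in the documents, and one constant hazard is applied to two different diseases. First dose to post-treatment Week 12 is not a fixed follow-up: it is 168 or 252 days for completers and shorter for early stoppers, whose visits run from last dose (stopping at day 14 ends it near day 14 + 84 = 98). And with 25 per cohort the intervals are wide, so comparison with outside experience would be weak.

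**Conclusion.** The point holds as a gap in reporting and data capture. All-cause death is nowhere a named endpoint. On-treatment deaths are mixed with other reasons for stopping, and deaths in the next 30 days sit within SAE or AE reporting. Deaths in the final 54 days of follow-up have no planned safety summary and, in completers, leave the primary safety endpoint a success. That final period is 32% of the study for 12-week subjects and 21% for 24-week subjects; these shares follow from the documents alone.

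The expected 0.4 to 3.1 deaths in that period depend on the assumed 5% to 40% annual mortality, a constant hazard, 50 dosed subjects and 12-week courses throughout. They show that the gap could matter; they do not predict a count. The change should be made because safety is the primary objective and the follow-up visits are already scheduled.

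**What to change.** 1. In sections 8.1.4 and 8.6, add all-cause death from first dose to post-treatment Week 12 in all dosed subjects, including those who stop drug or leave the visits. Record it with its date, irrespective of causality.
2. Report it by cohort and overall as n/N with exact 95% CI, with a listing of timing and recorded cause.
3. State that follow-up differs with treatment duration and early stopping, and show its length beside the count. A Kaplan-Meier estimate is optional.
4. Reconcile the entry rules in sections 7.1 and 7.2 with the SAE endpoint in the synopsis and section 8.1.4, so that fatal events are entered whether or not they led to discontinuation.

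The cost is one vital-status and date field, one table with its listing, and some record follow-up for subjects who leave the visits. No extra visit is needed.

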8.1.5. Analysis Conventions

All individual subject data will be listed as measured. All statistical summaries and analyses will be performed using SAS® software version 9.2 or higher (SAS Institute, Cary, North Carolina, USA). In general, all endpoints will be summarized with descriptive statistics by treatment group and analysis time point. For categorical variables, number and percentage of subjects in each category will be presented. Continuous variables will be descriptively summarized with n, mean, standard deviation (SD), median, Q1, Q3, minimum and maximum by treatment group. For SVR endpoints 95% confidence intervals will also be constructed.

8.2. Analysis Sets

8.2.1. Efficacy

The primary analysis set for efficacy analyses will include all subjects with HCV infection who received at least one dose of study drug.

8.2.2. **Safety**

The primary analysis set for safety analyses will include all subjects with HCV infection who received at least one dose of study drug.

8.3. Demographic Data and Baseline Characteristics

Demographic and baseline measurements will be summarized using standard descriptive methods by treatment arm and overall. Demographic summaries will include sex, race/ethnicity, stratification group, age. Baseline data will include a summary of body weight, height, body mass index, HCV genotype, and HCV RNA level (log₁₀ IU/mL).

8.4. Primary Analysis

The primary efficacy analysis will report the number and percent of subjects achieving SVR12 response will be calculated for each arm along with exact 95% confidence intervals.

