Screening assessments include physical examination with height and weight measurements, vital signs, medical history review for eligibility determination, safety laboratory tests, HCV RNA and HCV genotyping, HIV and HBV testing, serum β-hCG (females of childbearing potential only), ECG, and Fibroscan (if needed)

On-treatment assessments include adverse events (AEs) assessments, concomitant medications, physical examination, vital signs, safety laboratory tests, HCV RNA, ECG

Post-treatment assessments include adverse events (AEs) assessments, concomitant medications, physical examination, vital signs, safety laboratory tests, HCV RNA, ECG

Test Product, Dose, and Mode of Administration:

All study subjects will receive the sofosbuvir 400 mg and ledipasvir 90 mg fixed dose combination. Subjects will take one tablet in the morning.

Evaluation criteria Safety

AEs that lead to discontinuation, SAEs and safety laboratory tests will be collected until 4 weeks after the last dose of study drug. Safety endpoints will include

- Completion of full course of therapy
- Discontinuation for adverse events
- Serious adverse events

Efficacy

Efficacy will be evaluated using scheduled assessments of HCV RNA by PCR. All endpoints will be summarized with descriptive

statistics by cohort. Number and percent of subjects in each cohort will be presented for categorical variables. For continuous variables, N, mean, SD, Median, Q1, Q3, minimum and maximum will be presented.

The primary efficacy endpoint will be the SVR12 defined as HCV RNA < LLoQ for 12 weeks post-treatment.

GLOSSARY OF ABBREVIATIONS AND DEFINITION OF TERMS

AE adverse event

ALT alanine aminotransferase AST aspartate aminotransferase

BMI body mass index
BW Body weight
CLcr creatinine clearance

COPD Chronic obstructive pulmonary disease

CRF case report form(s)

dL deciliter

ECG electrocardiogram
e.g. For example
ET Early termination

FDA (United States) Food and Drug Administration

FDC Fix Dosed Combination FEV1 Forced expiratory volume

GCP Good Clinical Practice (Guidelines)

Hb hemoglobin

hCG human chorionic gonadotropin

HBV Hepatitis B virus HCV Hepatitis C virus

HIV Human Immunodeficiency Virus

ICF Informed Consent Form

ICH International Conference on Harmonisation

i.e. for explanation

ILD Interstitial lung disease
INR International normalized ratio
IRB institutional review board

LDV ledipasvir

LLoQ lower limit of Quantification MCV Mean corpuscular volume

mg milligram
mL milliliter

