8.5. Secondary Analyses

The proportion of subjects with HCV RNA below the LLoQ over time (including SVR endpoints) will be presented by treatment arm in tabular and graphical form.

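### Do the undefined terms arm and treatment group in Section 8 leave the two disease cohorts out of the planned tables?

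*Combined protocol and SAP*

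**What the plan says.** The Protocol Synopsis, under Evaluation criteria, gives the reporting rule: "All endpoints will be summarized with descriptive", continuing "statistics by cohort. Number and percent of subjects in each cohort will be presented for categorical variables". In the extracted text it falls under the Efficacy heading, although its wording is general.

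Section 8 uses other labels:

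- 8.1.5: "all endpoints will be summarized with descriptive statistics by treatment group and analysis time point". The sentence on continuous variables ends "minimum and maximum by treatment group. For SVR endpoints 95% confidence intervals will also be constructed".
- 8.3: baseline tables are given "by treatment arm and overall. Demographic summaries will include sex, race/ethnicity, stratification group, age".
- 8.4: the number and percent with "SVR12 response will be calculated for each arm along with exact 95% confidence intervals".
- 8.5: HCV RNA over time "will be presented by treatment arm in tabular and graphical form".
- 8.6: safety data are summarised by treatment arm, with a clause tying the arm to the drug that was received.

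Section 8.1.2 adds: "The primary safety endpoint is the proportion of subjects who complete a full course of therapy". Neither 8.4 nor 8.6 mentions that endpoint by name.

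On design, Sections 3.1 and 9.2.2 give all subjects the same fixed-dose combination. Section 3.3 plans about 25 subjects in each disease group. Section 3.4 sets separate entry criteria for each.

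**The concern.** The study has one drug and no randomisation, so arm has no obvious meaning. Two of the labels, read literally, lead away from the disease cohorts.

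First, 8.6 ties the arm to the drug received. With a single drug, that gives one safety group in which heart-failure and lung-disease subjects are mixed.

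Second, outside Section 8 the phrase treatment group appears only in the synopsis visit schedule, where it separates the 12-week from the 24-week subjects. Completion of a full course is the primary safety endpoint, and the only Section 8 grouping rule that plainly covers it is the general one in 8.1.5. A programmer could therefore tabulate the lead safety endpoint by duration.

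Section 8.3 also lists a stratification group, although the protocol describes no stratification.

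In a descriptive study the summary tables are the result. If they did not separate the cohorts, a reader could not see how each population tolerated treatment, and the protocol recruits the two populations separately.

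**Working it through.** **Planned sizes.** Section 3.3 gives 25 + 25 = 50, which agrees with the stated total of about 50. No power or precision calculation is given, so there is nothing further to reproduce.

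**Label count in Section 8.** Treatment group 2 (8.1.5), treatment arm 3 (8.3, 8.5, 8.6), each arm 1 (8.4): 2 + 3 + 1 = 6 uses in five subsections. Cohort: 0. Elsewhere cohort occurs 6 times: 4 name the two disease cohorts (synopsis and Section 3.4) and 2 state the synopsis reporting rule.

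**Synopsis against 8.1.5.** Both open with the same general sentence on summarising all endpoints descriptively. Both then give counts and percentages for categorical variables, and then the same list of statistics for continuous ones. 8.1.5 adds the analysis time point and the SVR confidence intervals. The only substitution is treatment group for cohort, so the same rule appears under two labels.

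**Each possible reading against each subsection.**

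| Section | One pooled group (about 50) | Duration (12 v 24 weeks, split not given) | Disease cohort (about 25 each) |
|---|---|---|---|
| 8.1.5 | Poor: a grouping is specified | Possible, from the synopsis visit schedule | Fits; parallel to the synopsis rule |
| 8.3 | Poor: a separate overall column would repeat the only group | Possible | Fits |
| 8.4 | Poor: each implies more than one | Possible | Fits |
| 8.5 | Possible | Possible | Fits |
| 8.6 | Literal reading | Fails: both durations take the same drug | Fits if the drug-received clause is ordinary as-treated wording |

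Pooling is the literal reading only in 8.6 and sits badly with 8.1.5, 8.3 and 8.4. Duration fails in 8.6. It has no planned group size, and the protocol body (Sections 3.2, 5.1 and 5.2) describes those subjects by length of treatment, never as treatment groups. Disease cohort can be used throughout.

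**What a misread table would hide.** Intervals are planned only for SVR endpoints, so the completion table would show counts and percentages. With assumed counts, 22 + 22 = 44 and 24 + 20 = 44, so both patterns pool to 44/50 = 88%. By cohort, the first is 22/25 = 88% in each; the second is 24/25 = 96% against 20/25 = 80%. A pooled row cannot tell these apart. The counts are illustrative and predict nothing.

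**What would be lost for good.** Nothing. 8.1.5 provides listings of all individual data, and each subject's cohort follows from the entry criteria met at enrolment. A table grouped the wrong way can be rerun by cohort from the same data.

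**The case for a change.** The strongest case for a change is that a programmer should not have to override the plan's own words. 8.6 names the drug received, and the synopsis visit schedule attaches treatment group to duration. These two places bear on safety and on completion of therapy, which together serve the primary objective. The by-cohort sentence may also be confined to efficacy by its position in the synopsis, so for safety the synopsis may not settle the matter. The edit would be a few words, and fixing the grouping beforehand removes any suspicion that it was chosen after seeing the data.

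Part of this stands. The labels are undefined and inconsistent, the literal sense of 8.6 is a single group, and stratification group refers to nothing in the protocol.

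The predicted mis-tabulation does not follow. The general sentence in 8.1.5 covers all endpoints and mirrors the synopsis rule, which is good evidence that the rule was meant generally. Completion is classed as a safety endpoint in the synopsis and in 8.1.4, so the all-safety-data sentence in 8.6 can be read to include it. The drug-received clause reads naturally as standard as-treated wording kept in a one-drug study. SVR12 is the least exposed table, since 8.4 calls for a result for each group. As for choosing the grouping late, the two disease groups, their sizes and their criteria are all fixed in the protocol beforehand.

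**Conclusion.** No change to the plan is needed. Section 8 carries the synopsis rule under inconsistent labels, and disease cohort is clearly the best-supported meaning. The effect is editorial: six uses of a loose term, with no test, threshold, sample size or planned interval method affected. At worst a safety or completion table would be laid out the wrong way and then rerun from the listed data.

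This rests on two assumptions: that the analyst reads Section 8 together with the synopsis and Section 3, and that each subject's cohort can be recovered from the eligibility record. Both are ordinary practice in a study of about 50 subjects. The remaining weak spot is 8.6, where the literal wording gives one pooled safety group; the rest of the document is enough to guide an analyst past it.
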